## 11.7 DATA COLLECTION

Electronic CRFs will be used to collect the clinical study data and must be completed for each enrolled subject with all required study data accurately recorded such that the information matches the data contained in medical records (e.g., physicians' notes, nurses' notes, clinic charts and other study-specific source documents). Authorized study site personnel (i.e., listed on the Delegation of Authority form) will complete eCRFs designed for this study according to the completion guidelines that will be provided. The Investigator will ensure that the eCRFs are accurate, complete, legible, and completed within 7 days of each subject's visit. At all times, the Investigator has final responsibility for the accuracy and authenticity of all clinical data.

All data should be substantiated by clinical source documents organized within a patient research record. ICH Good Clinical Practices are to be followed.

Electronic data for on study and follow-up patient data is submitted via the electronic system called REDCap. REDCap is managed from MUSC as a consortium partner under their CTSA. REDCap is a secure, Web-based application designed to capture and manage research study data.

The system has been reviewed for 21CFR Part 11 compliance and has been deemed "21CFR 11 Capable." Users of the REDCap system are limited to members of the IRB approved research team who are delegated data management responsibilities and those tasked with assuring quality control and quality assurance.

## 11.8 SUBSTUDY DATA COLLECTION

A data integration core has been established to integrate biological data (i.e., allostatic load) with information collected on social, psychological, behavioral, and clinical variables collected through the social determinants survey, MUSC's EPIC electronic health records (EHR), and MUSC's electronic data warehouse (EDW). This will be accomplished through several data integration strategies that will harmonize diverse types of data on psycho-social factors and biological biomarkers. These strategies include using natural language processing (NLP) techniques to identify social factors and patient stressors. Key data elements from the EHR and EDW will be extracted using NLP to establish discrete fields for patient demographics, encounter details, vitals, diagnostic history, medications, and laboratory results. Textual patient summaries such as clinical notes containing patient's social history will also be extracted from the EHR and EDW and analyzed via NLP. The Data Integration Core will also use data mining strategies to determine the temporal links between allostatic load and disease risk and outcomes in order to validate the associations observed in the study. All longitudinal patient data will be extracted from EDW via dynamic data pull (DDP) and from EHR using medical record numbers (MRNs) and stored in MUSC's REDCap data capture system and then merged with experimental data, and anonymized to create the main data repository. Anonymization will be performed by IRB certified honest brokers during integration of the data into the main data repository. Investigators will only have access to anonymized datasets. On a quarterly basis, data will be updated by honest brokers with any newly acquired clinical data items. Investigators will utilize the datasets to perform correlation analyses in order to examine linkages between biological, social, and clinical factors.

**APPENDIX A: SCHEDULED PROCEDURES AND ASSESSMENTS**

		Days on study f														
Therapeutic trial procedures	Procedure c	Pre a	1 n	15	29	57	85	113	141	225	309	393	477	561	645	730 g
	Informed Consent	X c														
	Full Physical Exam	X														
	Focused Physical Exam															
	Full Medical History	X														
	Interim Medical History o															
	AE assessment															
	CBCD	X														
	CMP	X														
	PSA	X m														
	Testosterone	X														
	CRP	X														
	Lipid Panel															
	CT (abdomen/pelvis)	X b														
	Tc-bone scan	X b														
	HIV test	X i														
	Hep B and C testing	X i														
Treatment	PROSTVAC-V															
	PROSTVAC-F															
Correlative Research	FACT-P															
	AUA															
	SHIM															
	Social Determinants Questionnaire															
	Research blood e															
	Research FFPE tissue	X i														
	Optional Sub-study Consent	X d														
Optional Sub-Study	Trier Stress Test	X i														

- a. Screening Assessments ("Pre") may be done up to 30 days prior to registration unless otherwise noted.
- b. Radiographic assessments may be done up to 26 weeks prior to registration. PSA at screening is required to document eligibility for post-operative PSA and may be done greater than 30 days prior to registration.
- c. The informed consent for the main study can be obtained more than 30 days prior to registration but must be obtained before any research procedures are completed
- d. The optional sub-study consent must be obtained prior to conducting the Trier Stress Test. The optional sub-study is voluntary and does not impact the patient's ability to participate in the main therapeutic portion of the trial.
- e. See [section 8](#) for blood draw volume and tube type requirements.
- f. all specified times are +/- 7 days
- g. or off-study day
- h. follow up will begin after the last day of study drug administration.
- i. Research blood, social determinants questionnaire and quality of life questionnaires may be completed any time after informed consent is signed and prior to Day 1 drug administration.
- j. If available: Send 5 thin (5 micron) sections on glass for H+E and IHC staining. These can be sent at any time after consent has been signed.
- k. Lipid panel requires patients to be fasting and can be done any time after informed consent is signed and prior to day 1 agent administration.
- l. HIV, Hep B and Hep C serology screening, unless known negative within previous 2 years prior to registration.
- m. PSA confirming eligibility can be done outside of the 30 day window. However, if PSA confirming eligibility was done greater than 30 days prior to day 1, it should be repeated prior to day 1 agent administration to ensure PSA is < 0.2ng/mL
- n. Day 1 assessments completed within 24 hours of screening assessments do not need to be repeated.
- o. Interim medical history includes any changes to the patient's medical history and/or any clinical changes since the previous clinic visit.
- p. For non-local patients in follow up, all attempts should be made to have subject return to the clinic for all follow up visits, but specifically day 225 and day 703. However, clinical care procedures (PSA, CMP, CBCD, focused physical exam and interim medical history – to include AE assessment and conmed assessment) may be done locally and the records provided. At a minimum, a PSA must be done and results provided to the study team. If a clinic visit is not done during follow up, the study team may conduct a phone interview (using the phone contact guide, Appendix D) in lieu of an clinic visit to assess adverse events, current cancer therapy and PSA level. Quality of life surveys may also be conducted over the phone by the study team if the subject does not return to clinic.
- q. Questionnaires may be mailed to the subject in pre-metered envelope if they are unable to come into the clinic to complete them (ie: due to COVID19 travel restrictions). The subject will complete the questionnaires at home and then mail the completed questionnaires back to the main site in the provided envelope.

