## 7.3 OFF-STUDY ASSESSMENTS

Off study assessments will consist of those procedures indicated for day 730 if the patient's participation ends at that time, or at any earlier time. These include:

- clinical examination (history and physical examination);
- assessment of toxicity or adverse events;
- CBCD;
- CMP
- bone scan and CT scan of abdomen, and pelvis (a Prostascint scan or MRI of abdomen, pelvis can be substituted). Scans will not be repeated at the off-study point if they have been performed in the preceding 2 months.
- PSA;

- total testosterone;
- research assessments
  - Blood samples-See Section 8 for details
  - Quality of Life questionnaires

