## 7.5 EFFICACY ASSESSMENTS

Efficacy assessments will primarily be performed by measurement of PSA and by physical assessment. Imaging studies (CT scans of the abdomen and pelvis, and bone scans) will be performed at baseline (up to 16 weeks prior to treatment) and at the end of the study (or within the preceding 2 months before end of study). Otherwise, scans will be performed only if clinically indicated for evaluation of relapse or off study. Additional forms of imaging (Prostascint scan, MRI) may be substituted for a CT scan of the abdomen and pelvis if clinically indicated. However, the imaging method used at baseline will be used for follow up scans. Compliance with therapy may be considered a component of the efficacy assessment. Compliance with PROSTVAC-V/F will be monitored at each visit by interviewing the patient and reviewing the infusion center records for administration.

Both primary and secondary efficacy assessment involve measurement of RFS. Recurrence will be defined as the occurrence of any of the following:

- Institution of new prostate cancer therapy
- First detection of a PSA level  $\geq 0.2$  ng/mL (confirmed  $> 30$  days later) after completion of all PROSTVAC V/F vaccine doses
- Development of radiographically-demonstrable metastases
- Death

RFS at two years will be met if a patient has met none of the above criteria two years post-surgery. RFS as a time to event endpoint will be measured as the time in days from surgery to any of the above conditions being met.

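### Appendix A note p sets a PSA-only minimum for non-local men that conflicts with the required end-of-study scans, leaves the two-year endpoint without a score when the scan is missing, and names Day 703 where the rest of the plan uses Day 730

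*Combined protocol and SAP*

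**What the plan says.** **Required imaging.** Section 7.3 states "Off study assessments will consist of those procedures indicated for day 730", and its list includes a bone scan and CT of abdomen and pelvis (or a permitted substitute). Section 7.5 calls for the same imaging at the end of the study or within the two months before it, using the baseline method. Section 7.3 likewise waives a repeat if scans were done in the preceding two months.

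**Endpoint.** One of the four relapse criteria in Section 7.5 is "Development of radiographically-demonstrable metastases". The scoring rule is "RFS at two years will be met if a patient has met none of the above criteria two years post-surgery".

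**Remote follow-up.** Note p of Appendix A asks that every attempt be made to have non-local men "return to the clinic for all follow up visits, but specifically day 225 and day 703". It then allows PSA, CMP, CBCD, focused examination and interim history to be done locally, and adds "At a minimum, a PSA must be done and results provided to the study team". If no visit takes place, the team may hold a phone interview "in lieu of an clinic visit to assess adverse events, current cancer therapy and PSA level".

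**Phone guide.** Appendix D is for men who do not return after the Day 141 dose. It asks about side effects, prostate cancer treatment, latest PSA and quality of life. The quality-of-life item is limited to Days 225 and 730, so the guide expects to be used at the final visit. It has no question about scans or metastases.

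**Window and missing data.** Appendix A note f reads "all specified times are +/- 7 days". Section 10.1 censors men without two-year data at their last recurrence-free visit.

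**The concern.** The final visit is when the primary endpoint is read, and the plan describes two levels of ascertainment for it. A man seen in clinic is assessed on PSA, new therapy, death and imaging. A man followed under note p's minimum can be assessed on the first three alone, and nothing in the note tells the site that the scan is still due. The endpoint rule then rewards the absence of evidence: a criterion that was never examined has not been met.

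This is a single-arm trial with a fixed count as its success rule (22 or more of 30), so a relapse visible only on an unobtained scan can move the result in one direction only, towards success. If such a man is treated as lacking two-year data instead, Section 10.1 censors him. That has meaning for the Kaplan-Meier curve but gives neither a success nor a failure for the binary test.

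A second, separate defect is that the one sentence telling sites which visits to protect names a day that is not in the calendar.

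**Working it through.** **1. Passages side by side, for a non-local man at the final visit**

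| Item | Sections 7.3 and 7.5 | Note p and Appendix D |
|---|---|---|
| PSA | required | required (the minimum) |
| New therapy | assessed | asked by phone |
| Bone scan and CT | required, or within the prior 2 months | not mentioned |
| Day | end of study; Day 730 in 7.3 | Day 703 in note p; Day 730 in Appendix D |
| Score if PSA present, scan absent | not stated | not stated |

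Note p neither waives the scan nor preserves it.

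**2. Day arithmetic**

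- Day 730 ± 7 runs from 730 − 7 = 723 to 730 + 7 = 737.
- Day 703 is 723 − 703 = 20 days before the window opens and 730 − 703 = 27 days before Day 730. A visit, PSA and research blood on that day are out of window.
- A scan 27 days before Day 730 is within the two-month allowance, so it remains acceptable.
- RFS is timed from surgery and Day 1 may be up to 120 days after it. Day 703 is therefore between 0 + 702 = 702 and 120 + 702 = 822 days after surgery. For a man starting 28 days or more after surgery it is at or past 730 days.

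**3. The plan's own operating characteristics**

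Inputs from Section 10.1: null 0.60, target 0.78, stop if 11 or fewer of 19, reject if 22 or more of 30, type I error 0.1, power 0.8. The rejection probability at true rate p is

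R(p) = Σ (x = 12 to 19) C(19, x) p^x (1 − p)^(19 − x) × P(Bin(11, p) ≥ 22 − x).

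- R(0.60) = 0.0934, within the stated 0.1.
- R(0.78) = 0.8007, matching the stated 0.8.

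The two-stage design reproduces.

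**4. Effect of missed scans, on assumed shares**

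Let f be the share of true two-year failures that only the final scan would show and that are missed. The documents do not give f. Assume 20% to 50% of men are remote at the final visit, all of them miss the scan, and 2% to 10% of relapses are visible only on imaging:

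- Low: f = 0.20 × 0.02 = 0.004. High: f = 0.50 × 0.10 = 0.05.
- Expected misclassified men under the null: 30 × 0.40 × f = 0.048 to 0.6.
- Apparent success rate under the null: 0.60 + 0.40 f.

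| f | Apparent rate | Two-stage type I error |
|---|---|---|
| 0 | 0.600 | 0.093 |
| 0.004 | 0.6016 | 0.096 |
| 0.02 | 0.608 | 0.109 |
| 0.05 | 0.620 | 0.136 |

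These figures also take 0.60 as the correct null under full scanning.

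**The case against.** **Note p does not waive imaging.** It lists what may be done locally, and scans are not on that list, so one may say Sections 7.3 and 7.5 still govern them. It also asks for every attempt at a clinic return. This stands as far as it goes: the plan does not delete the scan. But the note states a minimum, states it as PSA alone, and makes no exception for the final visit, and Appendix D provides for a Day 730 phone contact with no scan question. A site can follow the note and omit the scan. The calendar's post-baseline marks are not legible in the text available, so the cells to which note p is attached could not be checked; its wording covers follow-up visits generally.

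**Day 703 is a typing slip.** Very likely. The calendar, Section 7.3, Section 8.1 and Appendix D all use Day 730. A reader might infer that the wrong day causes a missing or invalid scan. It does not, because of the two-month allowance. Nor does it generally put the reading before two years, since the endpoint runs from surgery.

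**An unscanned man is not stated to be a success.** Correct. That is the natural reading of the scoring sentence, not written text, and Section 10.1 could be read as censoring him. Either way the binary test has no defined value for him.

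**The size is assumed.** This stands in full. Neither the remote share nor the imaging-only share is in the documents, and the calculation supposes that every remote man misses his scan. PSA, new therapy and death remain ascertainable remotely. The historical series behind 0.60 are described in Section 10.1 as differing in frequency and manner of follow-up, with no mention of a mandatory two-year scan, so fewer scans here might bring ascertainment closer to theirs. Inflation of the type I error is therefore possible, not shown.

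**Conclusion.** The concern holds in a limited form. Note p and Sections 7.3 and 7.5 are unreconciled on the end-of-study scan for non-local men, and the primary endpoint has no stated value for a man with a PSA but no scan. Separately, Day 703 conflicts with Day 730 elsewhere and places the visit, PSA and blood 20 days before the window opens.

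The numerical effect is probably small and cannot be determined from the documents. On the assumed range of 0.4% to 5% of relapses missed, the two-stage type I error goes from 0.093 to between 0.096 and 0.136, if 0.60 is the right null under full scanning.

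A reader might infer something stronger from the fact that lowering the single-stage bar by one man, from 22 to 21 of 30, moves the tail probability from 0.094 to 0.176. That figure needs one misclassified man with certainty, above the 0.6 expected at the top of the assumed range, and it uses a single-stage test where the plan's 22/30 rule is two-stage. It should not be taken as the size of the problem. The case for acting is that the gap is in the primary endpoint and is cheap to close.

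**What to change.** Reconcile note p with Sections 7.3 and 7.5 and the calendar:

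1. Replace Day 703 with Day 730.
2. State that the PSA-only minimum does not replace the end-of-study bone scan and CT (or permitted substitute) already required.
3. Allow that imaging to be done locally, by the method used at baseline, with the report sent to the study team. Add a line to Appendix D recording whether it was done, the date and the result.
4. In Section 10.1, state one primary binary score for a man who has a two-year PSA but no final scan; for example, not counted as recurrence-free in the 22/30 test. Make the alternative scoring a sensitivity analysis and report the number of such men.

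Cost: footnote and endpoint wording, with no added procedure because the scans are already required. The downside is collecting a few outside reports and, under the example scoring, a slightly more conservative estimate of two-year RFS.

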**APPENDIX B: SOURCE DATA FOR RFS**

*See next page for additional source of data for RFS*

E3886 Analysis for [name]

September 17, 2010

## Background

[name] conducted a study of adjuvant chemo-hormonal therapy in patients with high-risk prostate cancer and would like to compare progression-free survival (PFS) of the treated patients to the corresponding values from E3886.

## Key Eligibility Criteria

A total of 20 patients were enrolled in [name] study, and all of them had one or more high risk features for early relapse. High risk features included 1) pT3 or pT4 primary prostate cancer, or 2) one or more lymph nodes containing metastatic prostate cancer, or 3) detectable PSA ( $\geq 0.2$  ng/mL) after prostatectomy, or 4) an 84-month risk of relapse  $>40\%$  by the 1999 ~~Kattan nomogram~~.

In E3886, one hundred patients were randomized to either immediate androgen deprivation therapy (ADT) or deferred ADT. Two patients were ineligible due to no prior radical prostatectomy and no lymphadenectomy, resulting in 47 immediate ADT and 51 deferred ADT patients eligible for follow-up. To find a similar cohort from E3886 to evaluate PFS, the 98 eligible patients were evaluated for the high risk features listed above, and Table 1 shows the risk features in these patients. Ten (10%) patients had pT3a prostate cancer and 46 (47%) had pT3b disease. Due to limited information collected on this study, we were not able to determine whether a patient had pT4 disease or not. All patients had at least one positive node. Seventeen patients (17%) had detectable PSA after prostatectomy. The 84-month risk of relapse by the 1999 ~~Kattan nomogram~~ was not assessed for these patients. Based on the information above, all E3886 eligible patients ( $n=98$ ) had one or more high risk features and were included in the analysis.

## Statistical Methods

The method of Kaplan and Meier was used to characterize PFS for both [name] patients and E3886 patients. This report reflects the status of the E3886 database as of 2004. As the disease evaluation methods, assessment schedule, and follow-up duration were different between these two studies, no direct comparison was performed.

## Results

PFS is the endpoint of interest in this analysis. In [name] study, PFS is defined as the time from the date of prostatectomy until progression or death. Patients who were alive without documented progression were censored at the date of last disease assessment.

Progression is defined as either a rising PSA (PSA greater than 0.1 ng/mL in patients with an undetectable PSA after surgery) and/or the appearance of a suspicious new mass on an imaging study, preferably confirmed by an alternative study or biopsy.

In E3886, patients were randomized within 12 weeks after surgery, and PFS is defined as the time from study entry until progression or death. To make the definition of PFS consistent between the two studies, PFS for E3886 was recalculated from the date of radical prostatectomy to progression or death. Patients who were alive with no recorded progression were censored at the date they were last known to be progression-free. In this study, progression is defined as local recurrence, regional recurrence, distant metastases, PSA progression or death, whichever occurs first.

As the median follow-up was 11.9 years and 5.1 years among living patients in E3886 and [name] study, respectively, a 5-year PFS rate along with a 90% confidence interval (CI) was computed for each cohort. The 5-year PFS rate for [name] patients was 83% (90% CI, 62-93%; Figure 1). For E3886, the 5-year PFS rates were 83% (90%

E3886 Analysis for [name]

September 17, 2010

CI, 72-90%; Figure 2) and 27% (90% CI, 18-38%; Figure 3) in the immediate ADT and deferred ADT arms, respectively.

[figure not shown]
E3886 Analysis for [name]

September 17, 2010

Table 1: High Risk Features for E3886 Patients

	Immediate ADT (n=47)	Deferred ADT (n=51)
Pathologic T stage		
pT2	19 (40%)	23 (45%)
pT3a	6 (13%)	4 (8%)
pT3b	22 (47%)	24 (47%)
Nodal status		
Number assessed (median, range)	11(3-36)	14 (2-39)
Number positive (median, range)	2(1-19)	2 (1-20)
Postoperative serum PSA		
Range	<0.2-87.4 $\mu$ g/L	<0.2-48.7 $\mu$ g/L
Detectable	8 (17%)	9 (18%)

Figure 1: PFS for [name]

E3886 Analysis for [name]

September 17, 2010

Figure 2: PFS for E3886 Patients with Immediate ADT

[figure not shown]
[figure not shown]

Figure 3: PFS for E3886 Patients with Deferred ADT

**APPENDIX C: PROCEDURE FOR OBTAINING VIG AND CIDOFOVIR FOR TREATMENT OF SERIOUS ADVERSE REACTIONS CAUSED BY THE SMALL POX VACCINE.**

Information in this document is taken from the Smallpox fact sheet – Information for Clinicians and Public Health Professionals. The fact sheet can be reviewed in full here:

<https://emergency.cdc.gov/agent/smallpox/vaccination/pdf/mgmt-adverse-reactions-clinic.pdf>

